1. INTRODUCTION

“Initiation of a novel In-Hospital Treatment for Patients with Type 2 Diabetes (REMIT-2-D)”

This study will implement and rapidly optimize an in-hospital treatment package for people admitted to the Lyell McEwin Hospital (LMH), The Queen Elizabeth (TQEH) and Royal Adelaide (RAH) Hospitals with Type 2 Diabetes Mellitus (T2DM). In-hospital educational resources to develop diabetes-related health literacy have been shown to be of benefit and there are advantages to a healthy eating and exercise pattern.¹⁻⁹ Our aim is to test a simple, effective treatment package that can be delivered by non-doctor or non-nurse personnel but who are suitably trained in the delivery of the educational resources. The focus is on health literacy to improve self-care and connect to community support. We know that a comprehensive package is of benefit, but we don't know which components of the package drive the benefit.

The study is the second stage of the MRFF funded “Reducing Morbidity Mortality and Costs by Initiation of a novel In-Hospital Intervention for Patients with T2DM (REMIT-2-D)” project. Stage one of the REMIT-2-D project comprised: (i) an analysis of the patterns of admission, length of stay and re-admission of people with T2DM to the Lyell McEwin, The Queen Elizabeth and Royal Adelaide Hospitals; (ii) a systematic review of in-hospital interventions to improve outcomes for people with T2DM; (iii) focus groups with Aboriginal and Torres Strait Islander people who have T2DM and those who provide health care services to them and (iv) a more general group of health care professionals who provide services to people with T2DM.

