2. BACKGROUND

The Initiation of a novel In-Hospital Treatment for Patients with Type 2 Diabetes (REMIT-2-DS2) Project is one of several projects to receive funding in 2018 for one year through approved disbursements from the Medical Research Future Fund (MRFF) under its Rapid Applied Research Translation Program. The REMIT-2-DS2 project is the second stage of the “*Reducing Morbidity Mortality and Costs by Initiation of a novel In-Hospital Treatment for Patients with T2DM (REMIT-2-D)*” project, which received funding from the MRFF in 2017.

Type 2 Diabetes (T2DM) is a chronic condition that effects a large and growing proportion of the world's population. In Australia, it is the fastest growing chronic condition, increasing at a faster rate than other leading chronic diseases such as heart disease and cancer.¹⁰ The Australian Institute for Health and Welfare found that prevalence of T2DM tripled between 1989/90 and 2014/15 with around 1.2 million known and registered Australians currently living with diagnosed T2DM, and an estimated additional 500,000 people with silent, undiagnosed T2DM whilst indigenous Australian

adults are almost 4 times as likely to have T2D as their non-Indigenous counterparts.¹¹ If T2DM continues to rise at the current rates, it is estimated that up to three million Australians over the age of 25 years will have T2DM by the year 2025.¹²

There is a 50% risk the children of a parent with T2DM will have a genetic susceptibility to the condition. However, the risk of developing the disease is strongly related to excess stores of body fat (85 – 90% of all people with the disorder are overweight or obese), and strongly influenced by a range of psychosocial and lifestyle related factors¹⁰⁻¹³.

The complications of T2DM are serious and can include cardiovascular disease, stroke, kidney disease, limb amputation, depression, anxiety and blindness. Not only are the complications of T2DM preventable with good primary health care and in-hospital medical care, but the condition is preventable with appropriate lifestyle changes such as diet, exercise, smoking cessation, minimisation of alcohol consumption and stress management¹⁰.

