Appendix 3. Educational resources to develop diabetes-related health literacy

DIABETES SELF-CARE

THE WELLNESS WHEEL

BE HEALTHY

Healthy eating, regular activity, good sleep and a healthy mind

MEDICATIONS

Take your medications regularly. Learn about the drugs you are taking.

<https://www.nps.org.au/medical-info/consumer-info/managing-your-medicines>

PRIMARY CARE

Seeing a health professional regularly can identify problems early.

HEALTH CHECKS

Weight, blood pressure, HBA1C (average blood sugar over 3mths), blood fats and urinary protein

SELF-CARE

Understanding what's normal for you and knowing when to seek help

Foot care

- Check your feet every day
- Look for ulcers, swelling, blisters, bruising, cuts- seek medical help
- See a podiatrist

EYE CARE

- Have an eye test regularly
- Seek medical help if vision worsens

DENTAL CARE

- Have regular teeth and gum checks
- Quit smoking
- No sugary drinks

MONITOR YOUR HEALTH

Weigh yourself regularly, keep a diet and activity diary, check your blood sugars.

RESOURCES

Heart Foundation Helpline ph [name] and website: <https://www.heartfoundation.org.au/healthy-eating>

Diabetes Australia Helpline ph [name] and website: <https://www.ndss.com.au/>

Healthy Star rating: designed to show the nutritional content of packaged food, but it does not mean low in sugar or healthy. Fresh whole foods, mostly plants are best. Website: <http://healthstarrating.gov.au/internet/healthstarrating/publishing.nsf/content/home>

Get Healthy, ph [name] M-F 8am-8pm website: www.gethealthy.sa.gov.au

Keep Sight Australia, website <https://www.keepersight.org.au/>

The Sleep Health Foundation, P: [name], E: [contact], Website: <https://www.sleephealthfoundation.org.au/obstructive-sleep-apnea.html>

Sleep Health Service Clinics, SA Health, Locations:

Clinic B, level 2, Flinders Medical Centre, P: [name] or First Floor, Noarlunga GP Plus Super Clinic P: [name]

Adelaide Sleep Clinic, Wellington Centre, [name], P: [name]

E: [contact]

Centre for Physical Activity and Ageing, [name] Ph [name], website: [http://sacommunity.org/org/197186Centre for Physical Activity in Ageing](http://sacommunity.org/org/197186Centre%20for%20Physical%20Activity%20in%20Ageing)

Active Ageing Australia, [name], Ph: [name], email: [contact], website: <https://activeageing.org.au/>

[figure not shown]
Depression and Anxiety

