
Regular Dressings OR sauces (BBQ or Tomato) ____
 	
Sauces (Meal) ____
 	
Pre Made Lasagne ____
 	
Crumpets ____
 

Wholemeal Bread ____
 	
Mixed Rice Crackers ____
 	
Salt-reduced Stock ____
 	
Fruit Juice ____
 

Dried Herbs and Spices ____
 	
Deli style Metwurst or Pepperoni ____
 	
Frozen Vegetables ____
 	
Milk coffee sachets ____
 

Frozen Waffles ____
 	
Chuck Steak ____
 	
Hazelnut Chocolate Spread ____
 	
Shredded wheat cereals ____
 

Sample Time	Meal Occasion	Meal Suggestions		Average Cost (\$)
7-8am	Meal 1	
1-2 boiled eggs + 1 cup grilled veggies (i.e. carrot, capsicum, tomato, spinach, mushroom whatever is left in your fridge)
 	
150-200g plain or vanilla yoghurt + 40g nuts/seed mix added to the yoghurt for taste and crunch.
 	\$2.50
	Hydration	*[name] can they have a coffee no sugar?		
1230-1pm	Meal 2	
Small tin flavoured Tuna + 2 cups of salad mixed in a bowl (30g cheese optional)
 		\$4.00
	Hydration			
6-7pm	Meal 3	
150-200g of cooked meat, fish, chicken and 2 Cups of salad + 30g Cheese (optional) mixed into a tossed salad + veg (add 40ml of Free salad Dressing or Oil and vinegar for dressing)
 		\$5.70
	Hydration			
Nothing after 8 pm				

MUSCLE RESISTANCE ACTIVITY

[figure not shown]
THE WELLNESS WHEEL

PHYSICAL ACTIVITY IS LIKE TOOTHBRUSHING FOR THE WHOLE BODY

- We do it everyday
- Use every opportunity to **Move, Move, Move**
- Try tracking your activity using a Fitbit, phone app. or simple pedometer (aim for 10,000 steps/day).

BENEFITS OF MUSCLE RESISTANCE ACTIVITY

And let's do some Resistance Activity.

Resistance exercise can be done at home, even while watching your favourite TV show. It is easy, fun, free and suitable for anyone

Here are 4 movements for your upper body and 4 for your lower body

Upper Body

- Sit in a high back chair
- Make sure your bottom is right at the back of the chair and your back is straight
- Hold a 1 kg weight (see resource list) in each hand. If 1kg is too heavy use a can of sweetcorn or similar ~450 grams
- Do 20 repetitions of each of the movements pictured below. Rest briefly for 1-2 minutes then do another 20 of each movement. If you cannot manage 20, do as many as you can and gradually build up to 20.
- Do the movements slowly breathing in and out with each.
- Do these at least 3 days of the week. Build up to every day

Bicep

**Overhead
shoulder**

Straight arm

Side arm

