When you have completed the 2 lots of 20 repetitions of each of the 4 movements (or as many as you can do) stand and go for a walk for 10 minutes. Even if it is just around the house.

Now you are set to do the lower body

Lower Body

- For these you need 1kg strips of lead that are covered with material and have Velcro straps to fasten them around your ankles. You can also fill a small pouch with 1kg or 500 grams of course sand, attach some ties or Velcro straps so that one can be strapped around each ankle
- In the pictures below, you will see one of these exercises is done sitting in the chair as you for the upper body exercises. Two are done standing behind the chair and holding on. The final one is done lying on the bed. Maybe leave this one for last.
- Do 20 repetitions of each of the movements pictured below. Rest briefly for 1-2 minutes then do another 20 of each movement. If you cannot manage 20, do as many as you can and gradually build up to 20.
- Do the movements slowly breathing in and out with each.
- Do these at least 3 days of the week. Build up to every day.

**Knee
flexion/extension**

**Lateral leg
raise**

Toe lift

Straight leg raise

When you have completed the 2 lots of 20 repetitions of each of the 4 movements (or as many as you can do) stand and go for a walk for 10 minutes. Even if it is just around the house.

**IF AT ANY TIME YOU EXPERIENCE PAIN IN JOINTS OR THESE EXERCISES FEEL DIFFICULT,
PLEASE DISCUSS WITH YOUR HEALTH PROFESSIONAL.**

Here are some other ideas to help get you **moving moving moving**

Heart Foundation walking group join a group in your local area for free; phone [name] or [name] or go online at;

[Website: https://www.heartfoundation.org.au/support/heart-foundation-helpline](https://www.heartfoundation.org.au/support/heart-foundation-helpline)

Centre for Physical Activity and Ageing, [name] Ph [name], website:

[http://sacommunity.org/org/197186Centre for Physical Activity in Ageing](http://sacommunity.org/org/197186Centre%20for%20Physical%20Activity%20in%20Ageing)

Active Ageing Australia, [name], Ph: [name], email:

[contact], website: <https://activeageing.org.au/>

Exercise is Medicine- Australia- ESSA, Ph: [name], Email:

[contact], Website: <http://exerciseismedicine.com.au/>

Department of Health Be Active: a physical activity guide for older Australians.

Ph [name] or [name] or [name]- country

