There are various dietary approaches that may be suitable for people with diabetes. These include Mediterranean-style diets, low fat plant-based diets or lower carbohydrate eating plans.

The following guidelines are general recommendations suitable for most people with diabetes. However, a dietitian can help you to develop an eating plan to meet your food preferences and nutritional needs.

To make healthy food choices:

[figure not shown]
- eat regular meals to assist with managing energy and blood glucose levels
- choose high-fibre, lower glycaemic index (GI) carbohydrate foods
- limit foods that are high in saturated fat and choose healthy fats
- include lean protein foods with your meals
- choose foods low in added salt (sodium) and avoid adding salt to your food.

Eat regular meals in the right amounts

Aim to eat three meals during the day and choose serving sizes to meet your energy needs. Talk to your dietitian for advice about your individual needs and the serving sizes that are right for you.

When preparing a healthy meal aim to:

- fill half of your plate with a variety of non-starchy vegetables or salad
- fill a quarter of your plate (a palm-sized serving) with a lean protein source, such as lean meat, skinless poultry, fish, seafood, tempeh, legumes or eggs
- fill a quarter of your plate with a nutritious carbohydrate food that has a lower GI, such as wholegrain or legume pasta or noodles, brown, basmati or Doongara™ rice, quinoa, soba or mung bean noodles, legumes (such as chickpeas, kidney beans, lentils), barley, freekeh, corn, low-GI potato or sweet potato.

NDSS Helpline [name]

ndss.com.au

Physical activity

Regular physical activity is one of the most important things you can do to improve your health and help manage your diabetes.

The more physically active you are, the greater the health benefits will be. However, any activity, even at a slow pace, can have health benefits, and some activity is better than none at all.

Benefits of physical activity

Physical activity plays a vital role in helping the body use glucose as fuel for the working muscles, which in turn lowers blood glucose levels.

When the body starts to exercise, the muscles need energy to move. This energy comes from glucose in the blood as well as glucose stored in the muscles and, occasionally, from stores in the liver.

There are plenty of other benefits of regular physical activity, including:

- » reducing the risk of heart disease and stroke

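### The group 4 resistance leaflet tells inpatients with type 2 diabetes that weighted exercise suits anyone, and its readable text never advises checking before starting

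*Protocol*

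**What the plan says.** Section 9.b gives group 4, and no other group, the study's own muscle resistance sheet. That sheet (Appendix 3, Muscle resistance activity) recommends resistance exercise with the words "It is easy, fun, free and suitable for anyone". It then sets out hand-weight and ankle-weight movements, some of them upright ("Two are done standing behind the chair and holding on"), and after each block asks the patient to "stand and go for a walk for 10 minutes".

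After the lower-body block comes a caution in capitals: "IF AT ANY TIME YOU EXPERIENCE PAIN IN JOINTS OR THESE EXERCISES FEEL DIFFICULT", in which case the patient should talk to a health professional.

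Section 2 says that the complications of type 2 diabetes "can include cardiovascular disease, stroke, kidney disease, limb amputation, depression, anxiety and blindness". Section 7 includes adults admitted with type 2 diabetes. It excludes only those under 18, pregnant women, people unable to consent and people scheduled for coronary angiography.

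**The concern.** In this trial the leaflet is part of the intervention, so its wording is something that the protocol fixes. It makes an unqualified claim of suitability to a population in which the protocol itself expects conditions that call for care before weighted, partly standing exercise.

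The two triggers of the caution both depend on how the exercise feels. A patient who feels no pain and finds the movements easy meets neither, even if a foot ulcer, poor vision or a recent cardiac event would make it wise to ask first. What is at stake is avoidable exposure of a few patients to an unsuitable activity on the strength of a printed assurance.

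**Working it through.** No formula in the protocol bears on this, so the check sets the relevant texts side by side.

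1. **Claim against population.** The leaflet says the exercise suits anyone. Section 7 has no criterion on feet, vision, balance or past stroke, and its only cardiac-related exclusion is a scheduled angiogram. Section 2 names several of these problems as complications. The claim is therefore wider than the protocol's own description of the disease supports.

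2. **What the caution covers.** It has two triggers, joint pain and difficulty. Its opening words make it apply to the whole session, so its place on the page matters little. Its gap is in content: it responds to symptoms and does not ask for a check before starting.

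3. **Other text in the leaflet.** A lighter weight, fewer repetitions, slow movement and holding the chair are all offered. These adjust the dose for someone who finds the exercise hard. They do not alert someone who finds it easy.

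4. **Other material given to group 4.** The self-care sheet says of the feet: "Look for ulcers, swelling, blisters, bruising, cuts- seek medical help". That is useful advice, but it is not linked to the exercises.

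5. **Other sheets in the same appendix.** The national food-choices sheet limits itself to "general recommendations suitable for most people with diabetes" and points to a dietitian. The closer comparator is the national physical activity sheet. It encourages any activity and, in the text reproduced, has no check-first line either, but it does not claim to suit everyone.

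6. **Delivery.** Section 1 aims for a package that "can be delivered by non-doctor or non-nurse personnel", and the same sentence requires suitable training. Under section 9.b the coordinator helps with questionnaires that include medical history and collects data from the records. The written text states no use of these as an exercise check.

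7. **Planned exposure (section 10.a).** Stage 1 has 132 patients in four equal groups: 132 / 4 = 33 receive the leaflet. If group 4 is the arm retained, 33 more follow at stage 2: 33 + 33 = 66.

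**The case against.** The case against acting is fair in several respects.

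- The exercise is mild: about 450 g to 1 kg, seated, lying or holding a chair, and self-paced. The quoted line can be read as promotional copy.
- A trained coordinator delivers the material in person, in a session estimated at 30 minutes, after ward medical or nursing staff have identified the patient.
- Section 9.e promises medical assessment for any issue that a patient raises.
- Exercises that feel difficult is a broad trigger. It could take in breathlessness, poor balance or weakness after a stroke.

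All of this stands, and it keeps the point small. It does not remove it. Section 9.e acts only on what the patient raises, and a patient told that the exercise suits anyone has less reason to raise anything. The painless foot ulcer is the clearest case that these safeguards can miss.

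A reader might infer three stronger things that the documents do not support:

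- **That this is the leaflet's only caution, met only after the exercises are done.** The leaflet's figures are not shown, so this holds only for the readable text, and the caution is worded for the whole session.
- **That patients start without any medical check.** The study flow chart is also not shown and may contain one.
- **That the wording affects the HbA1c comparison or the error rates.** Nothing in the protocol suggests this.

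**Conclusion.** The point holds as a minor patient-safety correction. One unqualified statement in the group 4 leaflet is broader than the protocol's account of the patients supports, and the readable text has no check-first advice to balance it.

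Planned exposure is 33 patients, or 66 if group 4 is retained. The number with a medical reason for care is not in the documents, and no harm rate is estimated. The conclusion assumes that the missing figures add no check-first notice. If they do, only the suitability phrase needs changing.

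**What to change.** In the muscle resistance leaflet:

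- Replace the claim that the exercise suits anyone with wording such as *can be adapted to many abilities*.
- Before the first exercise, add one line, for example: *Check with your hospital team before you start if you have had a recent heart problem or a stroke, or have a foot ulcer, an amputation, or poor vision or balance.* The sponsor's clinicians should settle the list.
- Keep the existing caution.

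The exercises, eligibility and allocation stay as they are.

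The cost is an ethics amendment for one participant document. Section 10.a says that the sample size was cut because of low accrual, so recruitment appears to have begun. The leaflet version that each group 4 patient received should therefore be recorded. Some patients may start a little later within the six-week window, but the leaflet is delivered in hospital, where the treating team can be asked at once.
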